10.2 SETTING

10.2.1 Site selection

This active surveillance will be done at selected sites where IPF patients are regularly treated.

10.2.2 Selection of population

10.2.2.1 Inclusion / exclusion criteria

Inclusion criteria for nintedanib treated patients:

Inclusion criteria:

1. Patients with documented diagnosis of IPF based upon ATS/ERS/JRS/ALAT 2011 guidelines (nintedanib naïve or pirfenidone pre-treated) who have initiated or will initiate nintedanib according to the package insert after the commercial availability of drug in India (23rd January 2017).
2. Patients in whom it is possible to obtain voluntary informed consent either from the patient or patient's legally authorised representative (applicable for Group B and C patients, see [section 10.1](#) for details).

Proprietary confidential information © 2018 Boehringer Ingelheim International GmbH or one or more of its affiliated companies

3. Patients in whom data collection is possible from the medical records (applicable for Group A and B patients, see [section 10.1](#) for details).
4. Patients in whom information on baseline characteristics mentioned in the [section 10.3.3](#) is available.

-Exclusion criteria:

1. Patients who were previously treated with nintedanib.
2. Patients who have initiated or will initiate nintedanib concomitantly with pirfenidone.
3. Patients who are participating in a clinical trial.

Inclusion criteria for pirfenidone treated patients:

Inclusion criteria:

1. Patients with documented diagnosis of IPF based upon ATS/ERS/JRS/ALAT 2011 guidelines (antifibrotic naïve) who have initiated or will initiate pirfenidone according to the package insert after the commercial availability of nintedanib in India (23rd January 2017)
2. Patients in whom it is possible to obtain voluntary informed consent either from the patient or patient's legally authorised representative (applicable for Group II and III patients, see [section 10.1](#) for details).
3. Patients in whom data collection is possible from the medical records (applicable for Group I and II patients, see [section 10.1](#) for details).
4. Patients in whom information on baseline characteristics mentioned in the [section 10.3.3](#) is available.

Exclusion criteria:

1. Patients who were previously treated with nintedanib or pirfenidone.
2. Patients who have initiated or will initiate pirfenidone concomitantly with nintedanib.
3. Patients who are participating in a clinical trial.

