10.9 LIMITATIONS OF THE RESEARCH METHODS

The scientific objective of this active surveillance is to obtain an estimate of the occurrence of all ADRs and SAEs in IPF patients prescribed Nintedanib per the approved label in the real world setting. For retrospective data, there may be a possibility of missed information on adverse events. For patients followed prospectively, lost to follow up, loss of information and recall bias could impose limitations. Since only the cohort treated with Nintedanib will be followed up, it is impossible to assess the safety of Nintedanib compared to other drugs. The possible selection bias will be minimised by enrolling all patients who have initiated or will initiate nintedanib (Group A, B and C) from the date of commercial availability of drug (23rd January 2017) at selected centres and potential channelling bias will be assessed by recording the baseline characteristics of a comparator group of equal number of patients who have been treated with pirfenidone.

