## **7 PLANNED ANALYSIS**

- All study data will be included in individual patient study data listings. In general, all data will be listed by therapy prescribed and by visit (if applicable). The basic data like demographic and baseline characteristics, patient disposition and patient analysis set will be listed and also summarized by therapy prescribed, by Group. All summary tables will represent descriptive statistics for the parameters being analyzed, wherever applicable.
- Numeric presentations:
  - Non-integer numerical data should be presented with decimal point.
  - If the non-formatted data (e.g. which is received from the clinical database) is inconsistently presented, a decision on how to present the final data will be made on a case-by-case basis.
  - When rounding is required, number 4 or below will be rounded down and number 5 or above will be rounded up.
  - When deriving new variable(s) based on raw data, no rounding will be performed at intermediate calculation. Rounding will only be performed when displaying data.
  - Descriptive analysis for continuous data will include number of non-missing observations (n), mean, standard deviation (SD), median, minimum, maximum, Q1, and Q3. Means, medians, Q1 and Q3 will be rounded to 1 decimal place more than the original data. Standard deviation will be rounded to 2 decimals place more than the original data. Minimum and maximum will be displayed with the same decimal precision as the original data.
  - For categorical data, frequency and percentage with corresponding 95% confidence interval will be presented wherever applicable. Confidence interval and percentages will be rounded to 1 decimal place. Percentages equal to 100 will be output as '100'. The counts and percentages equal to 0 will be represented as '0' only.
- Missing data will not be imputed but will be analyzed as missing.

- Baseline assessments are the assessments taken at the Visit 1 for all patients. If there are multiple assessments collected on the same scheduled time, the average of these assessments will be used.
- The change from baseline is defined as the post-baseline value minus the baseline value.
- Text column should be left justified.
- All the data analysis will be done using SAS® version 9.4.

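### The baseline comparison used to assess channelling sets nintedanib patients who may be pirfenidone pre-treated against an antifibrotic-naive pirfenidone group, so unequal eligibility may be confounded with channelling.

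*Protocol*

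**What the plan says.** **Entry criteria (protocol 10.2.2.1).** The nintedanib group takes patients diagnosed under the "guidelines (nintedanib naïve or pirfenidone pre-treated) who have initiated or will initiate nintedanib", and its only exclusion for earlier treatment is "Patients who were previously treated with nintedanib". The pirfenidone group takes patients diagnosed under the "guidelines (antifibrotic naïve) who have initiated or will initiate pirfenidone according to the package insert", and excludes "Patients who were previously treated with nintedanib or pirfenidone".

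**Purpose of the comparator.** Protocol 10.9 states that "potential channelling bias will be assessed by recording the baseline characteristics of a comparator group of equal number of patients". Pirfenidone patients are not followed (protocol 10.1, 10.5), so the baseline comparison is their only analytic use. Protocol 10.7 compares the 200 pirfenidone patients with the nintedanib users, without restriction, and asks for caution where profiles differ.

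**Prior-treatment strata.** Protocol 10.7 also announces a subgroup analysis by prior treatment. Protocol 10.7.1 stratifies all analyses into (i) no earlier IPF drug, (ii) switch from pirfenidone, (iii) switch from another IPF drug and (iv) add-on to another IPF drug. Stratum (i) is decisive if results conflict.

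**SAP.** Under SAP 7, baseline data "will be listed and also summarized by therapy prescribed, by Group". Group there means enrolment timing (SAP 6.1). SAP 7.1 shows no split by prior treatment. SAP 7.2 lists prior IPF treatment for nintedanib patients only. SAP 4 declares no change from the protocol's planned analysis. SAP 6.4 is redacted.

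**The concern.** A baseline comparison shows channelling cleanly only if both groups could have contained the same kinds of patient. Here one group may contain second-line patients and the other may not. Patients who come to nintedanib after pirfenidone could plausibly have longer disease, lower lung function or a history of drug intolerance. If so, the nintedanib column moves on those variables even when prescribers choose between the two drugs without regard to patient profile among first-time starters.

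The protocol's background gives a reason to expect some such patients. It says that pirfenidone was the only drug registered for IPF in India and that many Indian patients do not tolerate it at recommended doses. It gives no share.

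At stake is how the comparator can be interpreted, not any incidence figure. If the overall table shows a difference, the reader cannot tell how much comes from choices between two first-line options and how much from the admission of second-line patients to one column only.

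**Working it through.** **The plan's own figure.** The 200 and 200 are a regulatory request (protocol 10.5) with no calculation behind them, so there is nothing to reproduce. The arithmetic below is only an illustration of size.

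**Inputs**
- n = 200 per group (protocol 10.5).
- s, the share of nintedanib patients pre-treated with pirfenidone: not in the documents; assumed 10%, 25%, 50%.
- d, the difference between pre-treated and antifibrotic-naive patients on a baseline measure, in SDs of naive patients: not in the documents; assumed 0.25, 0.5, 1.0.
- No channelling among naive patients, so the naive nintedanib and pirfenidone distributions are the same.

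**Formulas**
- Built-in difference: Δ = s × d.
- With equal unit SDs: SE = √(2/200) = 0.10 SD, and 95% half-width = 1.96 × 0.10 = 0.196 SD.
- With the mixture variance in the nintedanib group: SE = √[(1 + s(1 − s)d²)/200 + 1/200].
- Chance that the 95% interval excludes zero: Φ(Δ/SE − 1.96) + Φ(−Δ/SE − 1.96).
- Half-width using naive nintedanib patients only: 1.96 × √[1/(200(1 − s)) + 1/200].

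**One case in full.** With s = 0.25 and d = 0.5, Δ = 0.125. SE = √[(1 + 0.1875 × 0.25)/200 + 1/200] = 0.101. The chance is 23.5%.

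| s | Pre-treated of 200 | Δ at d = 0.25 / 0.5 / 1.0 (SD) | Chance interval excludes 0 | Naive-only half-width (SD) |
|---|---|---|---|---|
| 10% | 20 | 0.025 / 0.05 / 0.10 | 5.7% / 7.9% / 16.5% | 0.201 (180 v 200) |
| 25% | 50 | 0.0625 / 0.125 / 0.25 | 9.6% / 23.5% / 66.7% | 0.212 (150 v 200) |
| 50% | 100 | 0.125 / 0.25 / 0.50 | 23.8% / 69.2% / 99.7% | 0.240 (100 v 200) |

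The artefact is negligible if few patients are pre-treated. It dominates if many are and they differ strongly.

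**Which strata match the comparator.** The pirfenidone criteria bar earlier antifibrotics but allow earlier corticosteroids or N-acetylcysteine. Stratum (i) alone is therefore narrower than the comparator. Earlier nintedanib is excluded and earlier pirfenidone has its own stratum (ii), so strata (i), (iii) and (iv) combined approximate an antifibrotic-naive nintedanib set. The protocol does not say where a patient with both earlier pirfenidone and another IPF drug belongs, which is why the match is approximate.

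**Data available.** Previous IPF medication is mandatory at registration (protocol 10.2.2.3). Pirfenidone is named on that list, with dates, dose and reason for stopping (protocol 10.3.3).

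**The case against.** A reader might infer that the plan ignores prior treatment, or that built-in differences will be taken for channelling. The documents do not support either reading. Protocol 10.7 places the subgroup by prior treatment in the same section as the baseline comparison, 10.7.1 says the strata apply to all analyses, and pirfenidone switchers have their own stratum. No test or decision rule turns a difference into a finding of channelling; the protocol asks for caution. SAP 4 says nothing in the protocol's analysis has changed, and since SAP 6.4 is redacted, it cannot be said that the SAP lacks the strata. All of this stands.

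Nor is stratum (i) the only usable one, since patients with other earlier IPF drugs fall in (iii) or (iv). That no pirfenidone patient has earlier pirfenidone is also not a flaw in itself: any group of new starters has none of its own drug.

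The strongest objection is that moving a patient from pirfenidone to nintedanib is itself selective prescribing. The criteria permit such patients but do not require them. This stands in part, and it means switchers should not be discarded. But the mirror case, nintedanib to pirfenidone, is barred from the comparator, so the contrast that includes switchers has no counterpart and its size is hard to interpret.

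What the objections leave open is specification. The strata are listed under analyses of outcome events, which the comparator does not have. Nothing names the subset to be compared with the pirfenidone group, and the visible SAP baseline tables show no such split.

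**Conclusion.** The concern holds as a matter of specification. The comparison written in protocol 10.7 and 10.9 is whole group against whole group under unequal eligibility, so its differences may be confounded with channelling among first-antifibrotic starters. A like-for-like contrast is within reach of the protocol's own strata, but it is not tied to the baseline comparison.

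The size cannot be fixed from the documents. Under the assumed ranges it runs from 0.025 to 0.50 SD, and six of the nine cases lie below the 0.196 SD half-width. These figures rest on assumed shares and differences and show only that the artefact can be trivial or large. The primary and secondary outcomes concern nintedanib patients alone, and protocol 10.9 disclaims comparative safety, so no incidence estimate changes. This is a cheap improvement worth making, not a defect in the main results.

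**What to change.** In protocol 10.7 and SAP 7 and 7.1, specify the baseline table with three columns:
1. antifibrotic-naive nintedanib (strata (i), (iii) and (iv) combined);
2. pirfenidone pre-treated nintedanib (stratum (ii));
3. pirfenidone.

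Assign columns 1 and 2 by recorded earlier pirfenidone use, so that a patient with several earlier drugs has one clear place. Name column 1 against column 3, with standardised differences, as the like-for-like channelling contrast. Keep the overall nintedanib summary, and report column 2 separately as a distinct form of selective prescribing. If the redacted SAP section already defines these subgroups, a cross-reference to the baseline table is enough.

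The cost is wording and added table columns, with no new data, patients or change in eligibility. The naive column will hold fewer than 200 patients if any are pre-treated. The 95% half-width would rise from 0.196 SD to 0.201, 0.212 or 0.240 SD at assumed pre-treated shares of 10%, 25% or 50%.

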10.2.2.2 Registration period

There is no specific time frame for the enrolment period. It will end as soon as 200 patients are enrolled.

10.2.2.3 Patient registration method

In accordance with the inclusion & exclusion criteria, 200 IPF patients who have initiated or will initiate nintedanib (classified as Group A, B and C, see [section 10.1](#)) will be registered. In addition, 200 IPF patients who have initiated or will initiate pirfenidone (classified as Group I, II and III, see [section 10.1](#)) at the same centers and during the same time frame will also be registered.

The medical records at the selected sites will be screened to enroll Group A and B patients in a retrospective manner. Group C patients will be enrolled prospectively. The first patient enrolled at a given site should be in the nintedanib group. Once a patient is enrolled into the nintedanib group, the

site team is suggested to enrol the next eligible patient, who has initiated/will be initiating pirfenidone at the same site in the pirfenidone group.

Patients will be registered by entering following necessary information in the electronic data capture (EDC) system. This information will be mandatory for registration:

- Demographics
- Pulmonary function tests at visit 1 and further visits [FVC, FVC % predicted, FEV1 (mL), FEV1 % predicted, DLCO] – Yes/No/Unknown. If yes specify the values with the dates.
- Family history
- Time since IPF diagnosis (date)
- Chest HRCT evaluation (UIP pattern, Possible UIP pattern, Inconsistent UIP pattern, emphysema)
- Surgical lung biopsy (yes/no/unknown) (UIP pattern, probable UIP pattern, possible UIP pattern, inconsistent with UIP or non-classifiable, not available)
- Previous history of acute exacerbation (Yes/ No/unknown)
- Vital signs and physical examination [Heart rate (beats per minute), blood pressure (systolic blood pressure, diastolic blood pressure) weight and height] - available/not available/unknown, value, date.
- Symptoms
- Known hepatic/renal impairment (yes/no/unknown)
- Comorbidities at visit 1 (yes/no/unknown, if yes specify)
- Bleeding and thrombotic risk (yes/no/unknown)
- Previous medications for IPF (yes/no/unknown, if yes specify)
- Co-medications [at visit 1 and further visits (whether used or not, unknown, start and stop date and dose)]
- Laboratory tests at visit 1 e.g. LFT (performed/not performed/unknown/Performed but missing value and value, date)]

End of registration:

The patient registration at the selected centers will continue till 200 IPF patients treated with Nintedanib from the date of commercial availability of drug in India (23rd January 2017) are included; and their safety data are collected for at least 52 weeks or till the discontinuation of the drug, whichever is earlier. Baseline characteristics of 200 IPF patients treated with Pirfenidone at the same sites during the same period will also be collected.

10.2.3 Discontinuation of the study by the sponsor

A log of all patients included into the active surveillance study will be maintained at participating sites.

Boehringer Ingelheim India Pvt Ltd reserves the right to discontinue the study overall or at a particular study site at any point in time for the following reasons:

- Emergence of any new information on the safety of Nintedanib which mandates the discontinuation of the study
- Violation of the protocol, or the contract by a study site or investigator, disturbing the appropriate conduct of the study

The site will be reimbursed for reasonable expenses incurred in case of study termination (except in case of the second reason).

10.3 VARIABLES

10.3.1 Exposures

Exposure to Nintedanib will be estimated as time from the day Nintedanib is initiated until 52 weeks/ discontinuation of the drug (or the final contact with the patient for the last regular observation/end of the study).

Dosage and administration: Usually initial dose in adult patients is Nintedanib 150 mg twice daily; oral administration with food in morning and evening.

According to the Indian label the dosage should be reduced to Nintedanib 100 mg twice daily according to the patient's symptoms or in case of adverse events.

10.3.2 Outcomes

Safety

The primary outcome

- Incidence of all ADRs in nintedanib treated patients
- Incidence of all SAEs in nintedanib treated patients

Secondary outcome

- Percentage of patients who require dose reductions, interruptions and discontinuation due to adverse events.

How to assess and report AEs (including its definitions) are described in [section 12](#).

10.3.3 Other

Baseline characteristics

The following variables based on physician's report will be considered as the minimum baseline characteristics and potential confounders for the events of interest. The baseline characteristics will be recorded for all patients either prescribed nintedanib and pirfenidone from the same centre during the same time period. For the nintedanib treated patients certain information (e.g. co-medications) will also be collected at further visits, as the status may change over the time (see [flow chart](#) in the beginning of the protocol).

Demographics:

- Age
- Gender
- Weight
- Height
- Pregnancy status
- Smoking status
 - Never / Past / Current / Unknown
 - For the Past/Current, specify packs/year and for Past (number of years smoking one pack per day equivalent)
- Drugs of abuse
 - Alcohol (Drinker/ex-drinker/non-drinker/unknown)
 - Cocaine (Never/past/current /unknown)
 - Other (please specify)

Baseline characteristics of disease (date of assessment):

- Pulmonary function test (FVC, FVC % predicted, FEV₁ [mL], FEV₁ % predicted, DLCO) – Yes/No/Unknown, values and date
- Family history
- Time since IPF diagnosis (date)
- Chest HRCT evaluation (UIP pattern, Possible UIP pattern, Inconsistent UIP pattern, emphysema)
- Surgical lung biopsy (yes/no/unknown) (UIP pattern, Probable UIP pattern, Possible UIP pattern, Inconsistent with UIP, Not available)
- Previous history of acute exacerbation (Yes/No/Unknown)
- Vital signs and physical examination at visit 1 and further visits [yes/no/unknown, value, date, heart rate (beats per minute), blood pressure (systolic blood pressure, diastolic blood pressure; mmHg)].
- Symptoms (Dyspnoea on exertion (If yes, classify by modified MRC dyspnea scale (The classification are described in [ANNEX 3](#)), cough, clubbing, bibasilar crackles, weight loss, fatigue, dizziness, chest pain; whether or not)
- Known Renal impairment (yes/no/unknown)
Mild (Cr Clearance – 50-80 ml/min), moderate (Cr Cl – 30-49 ml/min) and severe (Cr Cl - <30 ml/min)
- Known Hepatic impairment (yes/no/unknown) by Child Pugh Score ([ANNEX 4](#))

Comorbidities: (yes/no/unknown, start/stop dates/ongoing)

- History of surgery within four weeks before administration
- Cardio and cerebrovascular comorbidities:
Arterial hypertension, coronary artery disease, myocardial infarction, congestive heart failure, ischaemic stroke, haemorrhagic central nervous system, transient ischaemic attack, peripheral artery disease, AF, other thromboembolic events (e.g. acute limb ischaemia, acute mesenteric ischaemia, renal infarction etc.), deep venous thrombosis, pulmonary embolism, pulmonary hypertension, Anemia, hemorrhage, Haemoptysis, haematuria
- Respiratory comorbidities:
Chronic obstructive pulmonary disease (COPD), emphysema (radiologic), asthma, pneumonia, obstructive sleep apnea, Respiratory failure, Renal comorbidities: chronic renal failure
- Hepatic comorbidities: cirrhosis, chronic hepatic failure
- Gastrointestinal comorbidities:

Gastroesophageal reflux disease (GERD), gastric ulcer, appendicitis, abdominal surgery, inflammatory bowel disease (e.g. Crohn's disease, ulcerative colitis), GI cancer, diverticulitis, superior mesenteric artery syndrome

- Metabolic comorbidities: Diabetes mellitus T1/T2, hyperlipidaemia, hypothyroidism
- Depressive disorder, anxiety disorder
- Neoplasms: Lung, liver, stomach, colorectal, breast and oesophageal, prostate and cervix cancer
- Others, please specify

Bleeding risk (unknown, no, yes – start date, stop date/ongoing, please specify)

- Genetic predisposition
- History of bleeding
- Gastrointestinal ulcers,
- Major injury or surgery
- Use of anticoagulants
- Others

Thrombotic risk (yes/no/unknown – start date, stop date/ongoing, please specify)

If yes:

- History of thrombosis
- Genetic predisposition (please specify)
- Trauma
- Immobilization due to injury or after surgery

Previous drug for IPF defined as usage before visit 1 assessment [whether used or not, unknown, start/stop dates, dosage, reason of discontinuation (side effects, physician's recommendation for alternative treatment)]:

- Pirfenidone
- N-acetylcysteine
- Corticosteroids
- Immunosuppressant (Azathioprine, Cyclophosphamide, cyclosporine A, others please specify)
- Others

Co-medications for IPF defined as at visit 1 and further visits (whether used or not, unknown start and stop date and dose, units):

- Pirfenidone
- N-acetylcysteine
- Corticosteroids
- Immunosuppressant (Azathioprine, Cyclophosphamide, cyclosporine A, others please specify)
- Others
- Co-medications:
 - Anticoagulant
 - Vit-K antagonist
 - Heparin
 - NOAC
 - Antiplatelet therapy (if yes high-dose antiplatelet therapy)
 - Aspirin (if yes please specify, if used as antiplatelet)
 - GERD medication
 - PDE-5 inhibitor
 - Endothelin receptor antagonist
 - Long-term Oxygen therapy

- Listed for lung transplantation
- NSAIDs
- Hormonal contraceptives
- Hormone replacement therapy
- Anti-VEGF drugs
- Chemotherapy
- Other, please specify

Laboratory tests at visit 1 (performed/not performed/unknown/performer but missing value and value (units), date):

- Liver function test (ALT, AST, GGT, ALP, Total Bilirubin)
- Other biochemical test (Cr, CK, BNP, CRP, LDH)
- Coagulation test (PT-INR, APTT)
- Immunological test (ANA, RF at visit 1 only)
- Urinalysis (Occult blood in urine by dipstick)
- Arterial blood gas (PaO₂, PaCO₃)

After visit 1, abnormal lab values that are clinically significant and related to Nintedanib will be collected as Adverse Event in eCRF and will be reported on NIS AE form.

[After visit 1, lab results will be collected in eCRF in following manner:

- Laboratory tests – done/not done/unknown
- If done – within normal range/unknown/out of range
- If out of range - clinically significant/clinically not significant
- If clinically significant – related to the Nintedanib/not related to Nintedanib
- If related to the Nintedanib – it will be reported on the AE page (In addition to the AE term, actual lab values that are abnormal, clinically significant & related to Nintedanib will also be reported in the CRF)]

In addition to this, any abnormal lab value, which is clinically significant and qualifies as SAE, will be reported in the eCRF and NIS AE form whether or not it is related to the Nintedanib.

